#### STATEMENT OF COMPLIANCE

The trial will be carried out in accordance with International Conference on Harmonisation Good Clinical Practice (ICH GCP) and the following:

• United States (US) Code of Federal Regulations (CFR) applicable to clinical studies (45 CFR Part 46, 21 CFR Part 50, 21 CFR Part 56, 21 CFR Part 312, and/or 21 CFR Part 812)

National Institutes of Health (NIH)-funded investigators and clinical trial site staff who are responsible for the conduct, management, or oversight of NIH-funded clinical trials have completed Human Subjects Protection and ICH GCP Training.

The protocol, informed consent form(s), recruitment materials, and all participant materials will be submitted to the Institutional Review Board (IRB) for review and approval. Approval of both the protocol and the consent form must be obtained before any participant is enrolled. Any amendment to the protocol will require review and approval by the IRB before the changes are implemented to the study. In addition, all changes to the consent form will be IRB-approved; a determination will be made regarding whether a new consent needs to be obtained from participants who provided consent, using a previously approved consent form.

# PROTOCOL SUMMARY

# 1.1 SYNOPSIS

TITLE:	An Investigation of the Antidepressant Effects of the mGlu2/3 receptor
	antagonist TS-161 in Treatment-Resistant Depression
STUDY DESCRIPTION:	This is a randomized, double blind, placebo-controlled, crossover, single–site study.  This experimental study will assess the efficacy and safety of three weeks of 50 to 100 mg/day of TS-161, an mGlu2/3 receptor antagonist prodrug.
OBJECTIVES:	Primary Objective:  The primary objective is to evaluate the ability of the mGlu2/3 receptor antagonist prodrug, TS-161, to improve overall depressive symptomatology in subjects with Major Depressive Disorder (MDD). The efficacy of a three-week course of TS-161 will be compared to three weeks of placebo in a crossover study. The Montgomery-Asberg Depression Rating Scale (MADRS) will serve as the main outcome measure.
	
 
Secondary Objectives:
 
To evaluate the antidepressant efficacy of TS-161 at 230 min, 1, 2, 3, 7, 14, and 21 days post-initial dosing compared to placebo in a crossover study, as assessed by change from baseline on MADRS total scores.
 
To determine whether TS-161 will demonstrate a superior antidepressant efficacy compared to placebo in a crossover study, as assessed by the proportion of subjects in remission (defined as MADRS total score ≤10).
 
To determine whether TS-161 will demonstrate a superior antidepressant response compared to placebo in a crossover study, as assessed by the proportion of subjects achieving response (defined as a ≥50% reduction from baseline in MADRS total score).
 
To evaluate the antisuicidal ideation effects of TS-161 at 230 min, 1, 2, 3, 7, 14, and 21 days post-initial dosing compared to placebo in a
 

	
 
2, 3, 7, 14, and 21 days post-initial dosing compared to placebo in a cross over study, as assessed by change from baseline on item 10 (suicidality) of the MADRS, the Columbia Suicide Severity Rating Scale (C-SSRS), and the Scale for Suicidal Ideation (SSI).
 
5. To investigate the effects of TS-161 on mood, anxiety, and anhedonia symptoms at 230 min, 1, 2, 3, 7, 14, and 21 days post-initial dosing compared to placebo in a cross over study, as assessed by change
 

Abbreviated Title: Antidepressant effect of TS-161 Version Date: 06 November 2023

6

[figure not shown]
	from baseline on the Hamilton Depression Rating Scale (HDRS), Hamilton Anxiety Rating Scale (HAM-A), Positive and Negative Affect Schedule (PANAS), Snaith–Hamilton Pleasure Scale (SHAPS), and the Temporal Experience of Pleasure Scale (TEPS) scales.  6. To assess the safety and tolerability of a three-week course of TS-161 compared to placebo in a crossover study, by incidence of adverse events (AEs) and total scores using the Clinician Administered Dissociative States Scale (CADSS), Young Mania Rating Scale (YMRS), the Brief Psychiatric Rating Scale (BPRS), vital signs,
	changes in clinical laboratory evaluations, and electrocardiograms (ECGs).
ENDPOINTS:	Primary Endpoint:
	Change from baseline in the MADRS total score
	Secondary Endpoints:
	
 
Proportion of subjects in remission (defined as MADRS total score ≤10).
 

	
 
Proportion of subjects with response (defined as ≥50% reduction from baseline in MADRS total score).
 

	
 
Change from baseline in HDRS, BPRS, CADSS, C-SSRS, HAM-A, PANAS, SHAPS, SSI, TEPS, YMRS total scores.
 

	• Incidence and nature of adverse events; vital signs; weight and body mass index (BMI) changes; physical examination changes; clinical laboratory evaluations; ECG.
	Surrogate Markers of Drug Effect, Target Engagement, and Antidepressant Response
	• Change in magnetoencephalography (MEG) spectral power (gamma power).
	• Change in glutamate levels in magnetic resonance spectroscopy (MRS).
	Change in resting and task based functional connectivity in fMRI.
	Change in peripheral biomarkers.
STUDY POPULATION:	Up to 25 individuals with Treatment-Resistant Depression (TRD) between the ages of 18 and 65 will be enrolled in the study. Participation will not be limited by gender identity or geographic location.
PHASE:	Phase 2 Proof-of-Concept (POC) Clinical Trial
DESCRIPTION OF SITES/FACILITIES	Research will be conducted at the NIH Clinical Center in Bethesda, Maryland, United States.

ENROLLING PARTICIPANTS:	
DESCRIPTION OF STUDY INTERVENTION:	This study will consist of a randomized, double-blind crossover administration of the mGlu2/3 receptor antagonist prodrug TS-161 (50 to 100 mg/day given orally) and placebo.
STUDY DURATION:	The estimated duration of this protocol is 36 months.
PARTICIPANT DURATION:	The total duration of the study, which consists of two phases, is 12 to 16 weeks.

# **1.2 SCHEMA**

# **Treatment Resistant Depression**

MDD (DSM IV or 5), ATHF  $\geq 1$  past failed trial, MADRS  $\geq 20$ 

# 1.3 SCHEDULE OF EVENTS

Timepoint i	Procedures
Phase I	Medication Taper, Drug-Free Period, and Baseline Assessments
Day -28 to Day - 15	Medication Taper
Day -14 to Day -1	Drug-Free Period
Day -8 to Day -2	Clinical Rating Scales ii Neurocognitive Battery Imaging : Structural neuroimaging studies (if clinically indicated, unless completed within the past 12 months), fMRI/MRS, MEG
Day -1	Clinical Rating Scale  Sample Collection: Safety Labs iii,iv  AE Assessments
Phase II	Research Conditions 1 & 2
Research Condition 1	
Day 0	
-60 to 0 min	Clinical Rating Scales ii AE Assessments Sample Collection: Research Blood, PK Blood Clinical Evaluations: Orthostatic Vital Signs, Height and Weight
0 min	Study Drug Administration: TS-161/ Placebo (100mg)
+60 min (1 hrs.)	Sample Collection: PK Blood
+120 min (2 hrs.)	Sample Collection: PK Blood Imaging: MEG

Timepoint i	Procedures
	Clinical Evaluations: Orthostatic Vital Signs
+180 min (3 hrs.)	Sample Collection: PK Blood
+230 min	Clinical Rating Scales ii AE Assessments Sample Collection: Research Blood
+240 min (4 hrs.)	Sample Collection: PK Blood Imaging: fMRI/MRS Clinical Evaluations: Orthostatic Vital Signs
+6 hrs.	Sample Collection: PK Blood Clinical Evaluations: Orthostatic Vital Signs
+8 hrs.	Sample Collection: PK Blood
+10 hrs.	Sample Collection: PK Blood
+12 hrs.	Sample Collection: PK Blood
Day 1	Clinical Rating Scales ii AE Assessments Sample Collection: Research Blood, PK Blood Study Drug Administration: TS-161/ Placebo (100mg or 50mg) v Clinical Evaluations: Orthostatic Vital Signs
Day 2	Clinical Rating Scales ii AE Assessments Neurocognitive Battery Study Drug Administration: TS-161/ Placebo (100mg or 50mg) v Clinical Evaluations: Orthostatic Vital Signs

Timepointi	Procedures
Day 3	Clinical Rating Scales ii AE Assessments Sample Collection: Research Blood Study Drug Administration: TS-161/ Placebo (100mg or 50mg) v Clinical Evaluations: Orthostatic Vital Signs
Day 4	Study Drug Administration: TS-161/ Placebo (100mg or 50mg) V Clinical Evaluations: Orthostatic Vital Signs
Day 5	Study Drug Administration: TS-161/ Placebo (100mg or 50mg) V Clinical Evaluations: Orthostatic Vital Signs
Day 6	Study Drug Administration: TS-161/ Placebo (100mg or 50mg) V Clinical Evaluations: Orthostatic Vital Signs
Day 7	Clinical Rating Scales ii AE Assessments Sample Collection: Research Blood, PK Blood, Safety Labs iii, エラー! ブックマークが定義されていません。 Study Drug Administration: TS-161/ Placebo (100mg or 50mg) v Clinical Evaluations: Orthostatic Vital Signs, Physical Exam
Day 8	Study Drug Administration: TS-161/ Placebo (100mg or 50mg) V Clinical Evaluations: Orthostatic Vital Signs
Day 9	Study Drug Administration: TS-161/ Placebo (100mg or 50mg) V Clinical Evaluations: Orthostatic Vital Signs
Day 10	Study Drug Administration: TS-161/ Placebo (100mg or 50mg) v Clinical Evaluations: Orthostatic Vital Signs
Day 11	Study Drug Administration: TS-161/ Placebo (100mg or 50mg) v Clinical Evaluations: Orthostatic Vital Signs
Day 12	Study Drug Administration: TS-161/ Placebo (100mg or 50mg) v Clinical Evaluations: Orthostatic Vital Signs
Day 13	Study Drug Administration: TS-161/ Placebo (100mg or 50mg) v

Timepoint i	Procedures
	Clinical Evaluations: Orthostatic Vital Signs
Day 14	Clinical Rating Scales ii AE Assessments Sample Collection: Research Blood, PK Blood, Safety Labs エラー! ブックマークが定義されていません。,エラー! ブックマークが定義されていません。 Study Drug Administration: TS-161/ Placebo (100mg or 50mg)v
	Clinical Evaluations: Orthostatic Vital Signs
Day 15	Study Drug Administration: TS-161/ Placebo (100mg or 50mg) Clinical Evaluations: Orthostatic Vital Signs
Day 16	Study Drug Administration: TS-161/ Placebo (100mg or 50mg) Clinical Evaluations: Orthostatic Vital Signs
Day 17	Study Drug Administration: TS-161/ Placebo (100mg or 50mg) Clinical Evaluations: Orthostatic Vital Signs
Day 18	Study Drug Administration: TS-161/ Placebo (100mg or 50mg) Clinical Evaluations: Orthostatic Vital Signs
Day 19	Study Drug Administration: TS-161/ Placebo (100mg or 50mg) Sample Collection: Urine pregnancy test Clinical Evaluations: Orthostatic Vital Signs
Day 20	Sample Collection: Research Blood, PK Blood, Safety Labs iii Neurocognitive Battery Imaging: fMRI/MRS, MEG Study Drug Administration: TS-161/ Placebo (100mg or 50mg) Clinical Evaluations: Orthostatic Vital Signs, Weight & Height, ECG
Day 21 to Day 34	Washout Period
Day 21	Clinical Rating Scales ii AE Assessments

Timepoint i	Procedures
Day 28 to Day 33	Neurocognitive Battery  Imaging: Clinical MRI, fMRI/MRS, MEG
Day 34 エラー! ブック マークが定義されていませ ん。 Research	Clinical Rating Scales ii Sample Collection: Safety Labs iii, エラー! ブックマークが定義されていません。 AE Assessments
Condition 2	
Day 35	
-60 to 0 min	Clinical Rating Scales ii AE Assessments Sample Collection: Research Blood, PK Blood Clinical Evaluations: Orthostatic Vital Signs, Height and Weight
0 min	Study Drug Administration: TS-161/ Placebo (100mg)
+60 min (1 hrs.)	Sample Collection: PK Blood
+120 min (2 hrs.)	Sample Collection: PK Blood Imaging: MEG Clinical Evaluations: Orthostatic Vital Signs
+180 min (3 hrs.)	Sample Collection: PK Blood
+230 min	Clinical Rating Scales ii AE Assessments Sample Collection: Research Blood
+240 min (4 hrs.)	Sample Collection: PK Blood Imaging: fMRI/MRS Clinical Evaluations: Orthostatic Vital Signs
+6 hrs.	Sample Collection: PK Blood Clinical Evaluations: Orthostatic Vital Signs

14

Timepoint i	Procedures
+8 hrs.	Sample Collection: PK Blood
+10 hrs.	Sample Collection: PK Blood
+12 hrs.	Sample Collection: PK Blood
Day 36	Clinical Rating Scales ii AE Assessments Sample Collection: Research Blood, PK Blood Study Drug Administration: TS-161/ Placebo (100mg or 50mg) v Clinical Evaluations: Orthostatic Vital Signs
Day 37	Clinical Rating Scales ii AE Assessments Neurocognitive Battery Study Drug Administration: TS-161/ Placebo (100mg or 50mg) v Clinical Evaluations: Orthostatic Vital Signs
Day 38	Clinical Rating Scales ii AE Assessments Sample Collection: Research Blood Study Drug Administration: TS-161/ Placebo (100mg or 50mg) v Clinical Evaluations: Orthostatic Vital Signs
Day 39	Study Drug Administration: TS-161/ Placebo (100mg or 50mg) V Clinical Evaluations: Orthostatic Vital Signs
Day 40	Study Drug Administration: TS-161/ Placebo (100mg or 50mg) V Clinical Evaluations: Orthostatic Vital Signs
Day 41	Study Drug Administration: TS-161/ Placebo (100mg or 50mg) V Clinical Evaluations: Orthostatic Vital Signs

Timepoint i	Procedures					
Day 42	Clinical Rating Scales ii AE Assessments Sample Collection: Research Blood, PK Blood, Safety Labs iii,エラー! ブックマークが定義されていません。 Study Drug Administration: TS-161/ Placebo (100mg or 50mg) v Clinical Evaluations: Orthostatic Vital Signs, Physical Exam					
Day 43	Study Drug Administration: TS-161/ Placebo (100mg or 50mg) V Clinical Evaluations: Orthostatic Vital Signs					
Day 44	Study Drug Administration: TS-161/ Placebo (100mg or 50mg) V Clinical Evaluations: Orthostatic Vital Signs					
Day 45	Study Drug Administration: TS-161/ Placebo (100mg or 50mg) V Clinical Evaluations: Orthostatic Vital Signs					
Day 46	Study Drug Administration: TS-161/ Placebo (100mg or 50mg) V Clinical Evaluations: Orthostatic Vital Signs					
Day 47	Study Drug Administration: TS-161/ Placebo (100mg or 50mg) V Clinical Evaluations: Orthostatic Vital Signs					
Day 48	Study Drug Administration: TS-161/ Placebo (100mg or 50mg) v Clinical Evaluations: Orthostatic Vital Signs					
Day 49	Clinical Rating Scales ii AE Assessments Sample Collection: Research Blood, PK Blood, Safety Labs iii ,エラー! ブックマークが定義されていません。 Study Drug Administration: TS-161/ Placebo (100mg or 50mg) v Clinical Evaluations: Orthostatic Vital Signs					
Day 50	Study Drug Administration: TS-161/ Placebo (100mg or 50mg) Clinical Evaluations: Orthostatic Vital Signs					
Day 51	Study Drug Administration: TS-161/ Placebo (100mg or 50mg) Clinical Evaluations: Orthostatic Vital Signs					
Day 52	Study Drug Administration: TS-161/ Placebo (100mg or 50mg)					

Timepoint i	Procedures					
	Clinical Evaluations: Orthostatic Vital Signs					
Day 53	Study Drug Administration: TS-161/ Placebo (100mg or 50mg) Clinical Evaluations: Orthostatic Vital Signs					
Day 54	Study Drug Administration: TS-161/ Placebo (100mg or 50mg) Sample Collection: Urine pregnancy test Clinical Evaluations: Orthostatic Vital Signs					
Day 55	Sample Collection: Research Blood, PK Blood Neurocognitive Battery Imaging: fMRI/MRS, MEG Study Drug Administration: TS-161/ Placebo (100mg or 50mg) Clinical Evaluations: Orthostatic Vital Signs					
Day 56 (or End of Study)	Clinical Rating Scales ii AE Assessments Sample Collection: Safety Labs iii,エラー! プックマークが定義されていません。 Clinical Evaluations: Urine Toxicology, Orthostatic Vital Signs, Weight, Height, ECG, Physical Exam					
Standard Treatment						
Up to 2 months	Standard Treatment					

i Allow up to 3 hours for procedures scheduled on the same day. Allow up to 3 days on procedures scheduled on different days to accommodate changes to the schedule. Some procedures may not be performed due to unforeseen technical or scheduling problems.

<sup>ii See the Schedule of Clinical Rating Scales for specific scales used.

iii See the Safety Labs section for a list of labs conducted.

<sup>iv A urine pregnancy test (HCG) will be obtained as indicated and no more than 24 hours prior to start of each research condition and imaging procedure. A urine toxicology screen will be obtained within 24 hrs of administration of study drug.

<sup>v See Dosing and Administration for more details on dose adjustments.

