mGlu2/3 receptor inhibition elicits rapid antidepressant actions in preclinical studies, similar to ketamine. In particular, a single administration of an mGlu2/3 receptor antagonist reduced immobility time in the 24-h forced-swim test (Dwyer, Lepack et al. 2012), decreased time delay until food consumption in the novelty-suppressed feeding test (Koike, Kasamatsu et al. 2013, Fukumoto, Iijima et al. 2014), rapidly reversed chronic stress-induced decreases in sucrose preference, which was sustained for at least 10 days (Dwyer, Lepack et al. 2013), and reversed

chronic corticosterone-induced behavioral deficits(Ago, Yano et al. 2013, Koike, Iijima et al. 2013) in rodents. In addition, mGlu2/3 receptor blockade reversed the decrease in sucrose preference and increased behavioral despair produced by chronic social defeat stress in mice within 24 hours after a single administration (Dong, Zhang et al. 2017). While a large (n = 310 subjects) clinical trial of a negative allosteric modulator of mGlu2/3 receptor (RG1578; decoglurant) failed to demonstrate antidepressant responses compared with placebo, no measure of target engagement was included in this trial and therefore we cannot conclude that the target was engaged. Additional studies are needed to determine the potential of mGlu2/3 receptor antagonists in the treatment of TRD (Quiroz, Tamburri et al. 2016). Both orthosteric and allosteric modulator for mGlu2/3 receptor have been shown to exert antidepressant effects, however the potency of allosteric modulators was demonstrated to be weaker than that of the orthosteric antagonists (Campo, Kalinichev et al. 2011). For this reason, we are pursuing investigation with a potent and selective mGlu2/3 receptor orthosteric antagonist.

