Surrogate Markers of Drug Effect, Target Engagement, and Antidepressant Response  1. To determine whether the glutamate peak in the medial PFC (mPFC) correlates with changes in depression scores to TS-161.  Hypothesis 1:  Among TRD-MDD subjects, pre-treatment mPFC glutamate levels will predict the magnitude of clinical improvement to TS-161 in subjects with MDD, but not to placebo.  Hypothesis 2:  Among TRD-MDD subjects, post-treatment increases in glutamate levels will predict the magnitude of clinical improvement to TS-161 (but not placebo).	1.  H-MRS correlates with changes in MADRS score	1. The MADRS is a tool used for the evaluation of depressive symptoms in adults and for the assessment of any changes to those symptoms. MRS is used to measure glutamate levels.
2. To determine whether gamma power increases with TS-161are associated with treatment response to TS-161.	Gamma power measured via MEG	MEG scanning is used to measure gamma power.
Hypothesis 1: Among TRD-MDD subjects, pre-treatment gamma power levels will predict the magnitude of clinical improvement to TS-161, but not to placebo.		

OBJECTIVES	ENDPOINTS	JUSTIFICATION FOR ENDPOINTS
Hypothesis 2: Among TRD-MDD subjects, post-treatment increases in gamma power will be positively associated with antidepressant response to TS-161 (but not placebo).		
3. To determine whether TS-161 modulates task-dependent and resting-state activity in the frontolimbic circuitry and whether changes in activity in the frontolimbic circuitry are correlated with antidepressant response to TS-161	3. Changes in activity in the frontolimbic circuitry	3. fMRI is used to measure frontolimbic circuitry
Hypothesis 1:  Among TRD-MDD subjects, TS-161 administration will increase pgACC activity and decrease amygdala activity to emotional faces more than placebo. Similar effects will be observed in activity associated with the restingstate networks. TS-161 will also decrease pgACC activity during the tasks more than placebo.		
Tertiary/Exploratory		
1. To determine whether TS- 161 will increase plasma/serum BDNF and vascular endothelial growth factor (VEGF) and decrease glycine/serine and alter oxidative stress/inflammatory parameters in peripheral	1. Plasma/serum BDNF, vascular endothelial growth factor (VEGF), glycine/serine, and oxidative stress/inflammatory parameters in peripheral leukocytes	1. To identify potential biomarkers of TS-161 antidepressant activity.

OBJECTIVES	ENDPOINTS	JUSTIFICATION FOR ENDPOINTS

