#### 8.2 MEDICATION TAPERING

If participants with MDD are medicated at the time of consent, they will undergo tapering of all prohibited medications (see Appendix B, Drugs Allowed and Not Allowed for details). The medication taper will be followed with a subsequent washout of two weeks during which time patients will be medication-free. Subjects will be reminded to report all medications, OTC products, and other agents to the investigators so that they can screen to avoid interactions that might make participation unsafe or might confound the research results. The taper off of medications and drug-free period of the study may be done as an outpatient if clinically appropriate. Medications that are required for non-psychiatric medical reasons (e.g., antihistamines and topical antifungals) will not be discontinued for the purpose of the study.

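### Baseline MEG, MRI/MRS and cognition can be done before washout is complete, and nothing re-times them when the Condition 2 washout is extended

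*Combined protocol and SAP*

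**What the plan says.** Section 8.2 sets the pre-study drug-free period: "The medication taper will be followed with a subsequent washout of two weeks during which time patients will be medication-free". Section 1.3 places it on Day -14 to -1 and schedules the first baseline cognition and imaging on Day -8 to -2, where the imaging entry ends "if clinically indicated, unless completed within the past 12 months), fMRI/MRS, MEG".

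Condition 1 dosing runs from Day 0 to Day 20. The Day 20 row still includes dosing: "Imaging: fMRI/MRS, MEG Study Drug Administration: TS-161/ Placebo (100mg or 50mg) Clinical Evaluations: Orthostatic Vital Signs, Weight & Height, ECG". Washout is "Day 21 to Day 34". Within it, the row for "Day 28 to Day 33" holds the second neurocognitive battery and "Imaging: Clinical MRI, fMRI/MRS, MEG". The next MADRS is on Day 34, followed by a pre-dose MADRS on Day 35 (section 1.4). Footnote i to section 1.3 lets procedures shift by up to 3 days.

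Sections 4.2 and 8.3 set 14 to 21 days between conditions to avoid carry-over. Patients who keep their response after two weeks get a third washout week; those still responding after that are withdrawn. Sections 8.4.2 and 8.4.3 provide six MEG and six MRI/MRS scans, with one baseline before each treatment phase.

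Section 3 uses these baselines directly. One hypothesis is that "pre-treatment gamma power levels will predict the magnitude of clinical improvement to TS-161, but not to placebo"; there is a matching one for glutamate, and others on post-treatment increases. Section 9.4 gives no imaging model and no definition of the imaging baseline.

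**The concern.** The plan sets its own standard for a clean start to each condition: two drug-free weeks. The MADRS baselines meet it. The imaging and cognitive baselines need not, and no reason is given.

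For a predictor hypothesis the baseline scan is the exposure variable; for a change hypothesis it is half of the outcome. Section 2.2.5 reports that in the group's ketamine work baseline gamma moderated, and at high values inverted, the link between post-dose gamma and response, so the state in which the baseline is taken matters. Section 2.2.2 also describes a behavioural effect of this drug class in rodents, after one dose, "which was sustained for at least 10 days". Here patients take 21 daily doses before the second baseline.

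The extended washout raises a further problem that needs no assumption about residual drug. Whether the extra week is needed is known only from the Day 34 rating, by which time the scan has been done.

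**Working it through.** **Inputs.** Drug-free period Day -14 to -1; first scan window Day -8 to -2; last Condition 1 dose Day 20; washout Day 21 to 34; second scan window Day 28 to 33; Condition 2 first dose Day 35; tolerance 3 days (all section 1.3). Interval 14 to 21 days, with an optional extra week (4.2, 8.3). Half-life of the active metabolite 1 to 5 h in rats and monkeys (2.2.10.3).

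**1. The plan's own figures reproduce.** Day -14 to -1 is 14 days, as in 8.2. Day 21 to 34 is 34 − 21 + 1 = 14 days, the lower end of the interval in 4.2.

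**2. Condition 1 baseline.** Full drug-free days before Day -8: −8 − (−14) = 6. Before Day -2: 12. Before the Day 0 scan: 14. If footnote i moves the scan to Day -11, only 3. Patients on the five-week washout in section 2.2.10 are already about 35 − 8 = 27 days out at Day -8.

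**3. Condition 2 baseline.** 28 − 20 = 8 days after the last dose; 33 − 20 = 13. With the tolerance, Day 25 is 5 days after. Days 28, 29 and 30 are 8, 9 and 10 days after, so 3 of the 6 permitted days fall at or within the 10-day rodent figure.

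**4. Extended washout.** The first dose moves to about 35 + 7 = Day 42. The scan is then 42 − 33 = 9 to 42 − 28 = 14 days old. Baseline, first-dose and end-of-condition scans make 3 per condition, or 6 in total, which is the number in 8.4.2 and 8.4.3. No repeat is provided for.

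**5. Residual drug.** 8 days is 192 h. At 5 h that is 192/5 = 38.4 half-lives, leaving 0.5^38.4 ≈ 3 × 10⁻¹². The available text gives no human half-life; at an assumed 24 h the residue is 0.5^8 ≈ 0.4%. Any carry-over would therefore be pharmacodynamic.

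**6. Which baselines TS-161 can reach.**

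| Sequence | TS-161-period baseline | Placebo-period baseline |
|---|---|---|
| TS-161 first | Day -8 to -2, before any TS-161 | Day 28 to 33, after TS-161: exposed |
| Placebo first | Day 28 to 33, after placebo only | Day -8 to -2, before any TS-161 |

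One of the four is exposed.

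**7. Direction of any bias.** Let D be TS-161's effect on a marker, c the fraction left at the exposed baseline and c′ the fraction left at the later placebo scan. With unadjusted change scores, the placebo change in the TS-161-first sequence shifts by −(c − c′)D and the drug-minus-placebo difference by +(c − c′)D. Averaged over equal sequences that is (c − c′)D/2. With c′ = 0 and c between 0 and 1, the average shift lies between 0 and D/2. The documents give no value for c, c′ or D, so this shows direction and limits, not a size.

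**The case against.** A reader might infer from the timing that baseline gamma and glutamate do carry prior-drug effects. The documents do not show that. The 10-day figure is rodent sucrose preference after another compound of the class. The marker evidence concerns ketamine within about a day: a trend-level glutamate rise at 24 h that the protocol reads as a sign of an earlier change (2.2.6), and resting gamma increases at six to nine hours (2.2.5). Nothing reports either marker at 8 days. This objection stands: the claim is that the baselines may carry such effects.

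A reader might also infer that the predictor of TS-161 response is contaminated by TS-161. The table in the working rules that out. Patients still responding after the third week are withdrawn, so the most persistent responders contribute no Condition 2 change. This stands too.

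The Condition 1 concern applies only to patients tapered off medication. Recovery from withdrawal falls on both randomised sequences alike, so it adds noise or a period effect, not a directional drug-placebo bias.

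On the extended washout, it can be said that section 1.3 shows only the 14-day case and that staff might simply rebook. Nothing tells them to, and the decision follows the scan. Sections 4.2 and 8.3 also say that responders at the end of the first condition do not cross over; read literally, that would remove the extended-washout case. It sits beside the sentences describing the extra week, and the two need reconciling.

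Finally, the scans and cognitive tests are headed optional, and section 2.2.5 calls MEG gamma exploratory. That limits the weight of the point but does not remove it.

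**Conclusion.** The point holds as a scheduling defect in the surrogate-marker and cognitive aims. Baselines may be taken with 6 to 12 of 14 drug-free days complete, or 8 to 13 days after the last Condition 1 dose. For a patient given the extra week, the Condition 2 baseline is 9 to 14 days old at first dosing and was taken while response persisted. The age of the scan is separate from drug carry-over and can arise in either sequence.

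Carry-over of TS-161, if there is any, threatens the placebo change and the contrast between TS-161 and placebo in the TS-161-first sequence. It does not threaten the baseline that predicts TS-161 response. Its size cannot be stated. The MADRS endpoints are unaffected.

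This rests on the nominal schedule being followed, on the extra-week rule being the operative one, and on no imaging-baseline rule existing outside this document.

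**What to change.** In section 1.3, place baseline imaging and cognition in the last four days before each condition's actual first dose: nominally Day -4 to -1 and Day 31 to 34. State that footnote i may not move scans earlier than that window; otherwise Day 31 could slip back to Day 28. This gives 10 to 13 full drug-free days before the first baseline, and 11 to 14 days from the last dose to the second.

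For Day 21 responders, schedule the Condition 2 baseline after the Day 34 MADRS. If the washout is extended, the scans are then deferred to the last days before the actual first dose (about Day 38 to 41) instead of being repeated. Define the scan in that window as the condition's imaging baseline.

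The number of scans is unchanged. The cost is a four-day booking window in place of seven days (Condition 1) or six (Condition 2), and perhaps a few missed optional scans. Day 21 responders whose washout is not extended have Day 34 alone for MEG, MRI/MRS and cognition; the schedule already combines all three on Days 20 and 55. The window still lies inside the washout, and Day 31 is not clearly beyond an effect lasting 10 days or more, so this reduces the exposure without abolishing it. Because scan timing in Day 21 responders would depend on Condition 1 outcome, report it by sequence.
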